2.1. Background and rationale

About one-third of all critically ill patients suffer from circulatory shock, which places them at increased risks of multi-organ failure, long-term morbidity, and mortality (1,2). Combinations of clinical, haemodynamic and biochemical variables are recommended for establishing the diagnosis and instigation of treatment (3,4). If necessary, more advanced and sequential haemodynamic assessments using critical care ultrasound (CCUS) as preferred modality are recommended (3-6).

Clinical examination in the critically ill comprises frequent measurement of heart rate, blood pressure, body temperature, skin perfusion, urine output and mental status (3). Daily use of clinical examination (in any patient) for diagnostic purposes contrasts with the limited number and quality of studies, so that the level of evidence for use of clinical examination in the critically ill is considered best practice (3). Previous studies have suggested different prognostic or diagnostic variables and many studies have analysed single or dual variable associations, while no research has evaluated their additional value on top of the accepted predictors (7). The reason for inconsistency of results in these studies potentially originate from several methodological flaws, including improper research design, lack of confirmation cohorts, and power and sample size issues.

The additive diagnostic and prognostic value of combinations of clinical, biochemical and haemodynamic variables remains to be established with a higher quality of evidence. These variables have never been evaluated collectively in a large, broad, prospective cohort of critically ill patients. Therefore, we established the Simple Intensive Care Studies I (SICS-I) with the aim to evaluate the diagnostic and prognostic value of a comprehensive selection of clinical and haemodynamic variables in the critically ill (7).

Prospective registration of protocols of observational studies are promoted to prevent outcome reporting bias (8,9). Likewise, prospective publication of a detailed statistical analysis plan (SAP) is encouraged to prevent data-driven analyses (9-11).

2.2. Objectives

2.2.1. Objectives and research questions

The objective of the SICS-I study was to establish a cohort with a dual aim: to evaluate the (1) diagnostic and (2) prognostic value of a comprehensive selection of clinical examination, haemodynamic and biochemical variables in the critically ill. More specific, the two research questions of the basic study were (1): which combination of clinical examination findings is associated with cardiac index measured

with CCUS? And (2): which combination of clinical examination, haemodynamic and biochemical variables is associated with 90-day mortality?

In the basic study of the SICS we collected a broad number of clinical examination, haemodynamic and biochemical variables, and used CCUS to only measure cardiac output. The infrastructure and design enabled (temporarily) addition of sub-studies in which additional variables were collected. Research questions of the sub-studies all address the overall aim of the SICS-I cohort (**table 1**).

2.2.2. Hypotheses

The hypothesis of research question 1, i.e. the diagnostic study, are:

- Null hypothesis: there is no true correlation between any single or a combination of clinical examination findings and cardiac index measured with CCUS
- Alternative hypothesis: cardiac index measured with CCUS is associated with one or a combination of clinical examination findings

The hypothesis of research question 2, i.e. the prognostic study, are:

- Null hypothesis: clinical examination, biochemical and haemodynamic variables are not associated with 90-day mortality
- Alternative hypothesis: clinical examination, haemodynamic and biochemical variables are associated with 90-day mortality

2.2.3. Scope

This SAP will be the guiding document for the analyses that will be conducted in the basic study. We intend to present the results of the two primary aims in separate manuscripts. All the aims and research questions of the sub-studies will be included in the appendix of this SAP, and we aim to present the SAPs of the sub-studies as an addendum in the future.

3. Study methods

3.1. General study design and plan

The SICS-I is a prospective cohort study which is conducted in the department of critical care of the University Medical Center Groningen (UMCG). The entire study was purely observational in design; no interventions were applied as part of the study protocol.

The protocol of this study was published on the website of the department of critical care of our hospital before the start of the study (Project number: 201500144) and registered at clinicaltrials.gov (NCT02912624). This analysis plan has been written while data collection was ongoing, but before full access to the study database. For our design paper, we only extracted baseline data and we did not have access to the validated outcome data.

3.2. Sample size, power and detectable difference

There are no previous studies which included combinations of clinical examination, haemodynamic and biochemical variables into one model for estimation of cardiac output and mortality. This makes it difficult to calculate sample size based on previous literature. Alternatively, we made an estimation of the power of our multivariable models given the set sample size of our cohort.

3.2.1. Diagnostic study

We are planning our main analysis with 1075 patients in which we will regress their values of cardiac index against clinical examination findings. For this power calculation, we used the clinical examination variables urine output and capillary refill time as an example (7). In our design paper, the SD of cardiac index was 0.99 and the SD of urine output was 0.98, with a slope estimate of 0.040 obtained when cardiac index was regressed against urine output. The SD of capillary refill time was 2.4, with a slope estimate of -0.045 obtained when cardiac index was regressed against capillary refill time. If the true slope of the line obtained by regressing cardiac index against urine output or capillary refill time is 0.10, we will be able to reject the null hypothesis that this slope equals zero with probability (power) 0.81 for urine output, and 1.00 for capillary refill time. The type I error probability associated with this test of this null hypothesis is 0.015 (see paragraph 6.6 below).

3.2.2. Prognostic study

We are planning our main analysis with 1075 patients and take skin mottling as an example for our power calculation: in our design paper, 46% of the patients has skin mottling. If we assume a similar proportion in our total cohort, we have 495 patients with skin mottling and 580 without. Pilot data from our design paper indicate that the 30-day mortality proportion among controls is 0.18 (7). If the true mortality proportion for patients with skin mottling is 0.27, we will be able to reject the null

hypothesis that the mortality proportion for patients with skin mottling and control patients are equal with probability (power) 0.84. The type I error probability associated with this test of this null hypothesis is 0.015. We will use an uncorrected chi-squared statistic to evaluate this null hypothesis.

3.3. Timing of final analysis

Data cleansing and CCUS image validation will be performed upon completion of the 90-day follow-up of the last patient included in the study. The final analysis will be conducted hereafter.

This statistical analysis plan was added to the study protocol at clinicaltrials.gov, before closure of the database and before any analyses had been conducted. Independent study monitoring was conducted in adherence to the Good Clinical Practice guidelines (10).

3.4. Timing of outcome assessments

Follow-up on all-cause mortality was conducted at 1 November 2017, i.e. 90-days after the inclusion of the last patient.

4. Statistical principles

4.1. Multiplicity

The diagnostic and prognostic basic study and each sub-study consist of one primary outcome and one or more secondary, exploratory outcomes. We will encounter multiplicity issues due to the multiple primary outcomes that are tested for significance in the same cohort. The SICS-I cohort addresses six different primary outcomes (table 2, last column); two primary outcomes of the basic study (diagnostic and prognostic), and four additional outcomes in the nine sub-studies.

We will apply an adjustment for multiplicity based on the total numbers of different primary outcomes tested. Our cohort mainly addresses haemodynamic research questions, so that most outcomes will probably be positively correlated. Therefore, a Bonferroni adjustment of the P-value might be too conservative. We chose for multiplicity adjusted thresholds by following the pragmatic approach stated by Jakobsen et al. (12). The authors suggested that the ‘true’ threshold lies somewhere between the unadjusted threshold (most often 0.05) and the Bonferroni adjusted threshold. Where in this interval the ‘true’ threshold is placed is dependent on the correlation between the outcomes, if two outcomes are perfectly correlated (a correlation coefficient of 1) no adjustment of the threshold for statistical significance is needed, if two outcomes are totally independent (a correlation coefficient of 0) a full Bonferroni adjustment is needed. Therefore, Jakobsen et al suggest “dividing the pre-specified P-value threshold with the value halfway between 1 (no adjustment) and the number of primary outcome comparisons (full Bonferroni adjustment)” as such an adjustment will come closer to the ‘true’ statistical significance level than the ‘extreme thresholds’ in a majority of situations (12). The corresponding formula is:

$$\textit{Threshold for significance} = \frac{\alpha}{\left(\frac{m+1}{2}\right)}$$

Wherein:

- α is the unadjusted threshold for significance, usually 0.05
- m is the number of primary outcomes or tests (used) in the same cohort (in this case: six)

The threshold for significance in the SICS-I cohort will be:

$$\textit{Threshold for significance} = \frac{0.05}{\left(\frac{6+1}{2}\right)} = 0.0143 \approx 0.015$$

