4.2. Statistical significance and confidence interval

As calculated in 4.1, we will consider a $P < 0.015$ as statistically significant for our primary outcomes. When we find a $0.015 \leq P \leq 0.05$, we will consider this association of dubious significance and will emphasise the increased chance of a type I error. Results will be presented with their values (e.g. regression coefficients, odds ratios, etc.) with 98.5% confidence intervals.

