6.2. Analysis methods

6.2.1. Correlations

We will use the Pearson *r* correlation and Spearman correlation coefficient rho (*r*) to evaluate the degree of relationship between variables. For normally distributed variables, we will use the Pearson *r* correlation with 98.5% confidence interval upon checking for linearity and homoscedasticity, while in case of skewed, ordinal data, the degree of association between variables will be quantified using Spearman correlation coefficient rho (*r*). We will use Cohen's *d* to evaluate the correlation coefficient and assess the strength (or effect size) of the relationships, where a correlation coefficient between

0.10 and 0.29 will represent a small association, between 0.30 and 0.49 a medium association, and a coefficient of 0.50 and above a large association.

6.2.2. *Continuous and dichotomous outcomes (diagnostic study)*

We will conduct a least-squares linear regression analysis for continuous dependent variables and a logistic regression for dichotomous dependent variables. A univariable regression analysis will be conducted on 17 clinical examination findings with cardiac index as the dependent variable. A univariable regression analysis will be conducted on all variables and a $p < 0.25$ will be used for inclusion in the multivariable model. As there are no previous studies that include (a combination of) all available clinical examination variables into one model estimating cardiac index, we will not include any variable on a theory driven basis. We will construct the multivariable model using forward stepwise regression by adding blocks of variables. In case of a multivariable linear regression model, we will construct a kernel density plot to assess normality of the residuals and check the homogeneity of variance by plotting the residuals versus the fitted values. We will use the variance inflation factor (VIF) to check for multicollinearity; as a rule of thumb, we will assume multicollinearity when a variable has a VIF-value greater than 10. If the assumptions are not met, we will use an ordinal regression analysis.

6.2.3. *Time-to-event data (prognostic study)*

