Analysis of mortality will be performed using time-to-event data (patients were censored at 90-days of follow-up). Categorical variables will be analysed using the log-rank test and continuous variables will be assessed using a univariable Cox proportional hazard regression analysis. Analysis of mortality proportion will be presented by Kaplan-Meier survival curves when independent variables are dichotomous or categorical. A univariable Cox regression analysis will be conducted on 22 clinical examination, haemodynamic and biochemical variables with 90-day mortality as the dependent variable. Covariates with a $p < 0.25$ in the univariable analysis will be included in the multivariable model. We will include the SAPS-II score in our multivariable Cox regression model of 90-day mortality. The SAPS-II is a predictive score for in-hospital mortality and includes seventeen covariates among which age, haemodynamic and biochemical variables, and presence of metastatic or haematological cancer (21). The proportionality assumption will be tested by using the Schoenfeld and scaled Schoenfeld residuals. We will test the proportionality of the model as a whole and the proportionality for each predictor and reject proportionality in case of significant test findings ($p < 0.05$). We will plot graphs of the scaled Schoenfeld assumption, where horizontal lines in the graph indicate that the proportionality assumption is not violated. We will also construct log-log plots, where two parallel lines indicate that proportionality was not violated. The goodness of fit of the final model will be evaluated

by using the Cox-Snell residuals. In our Cox regression models, at least 15 events are necessary for each variable included in the final model (22,23).

6.2.4. *Validation (both)*

Because of the fixed sample size of our study, we will use bootstrapping validation to assess the accuracy of our model. We will randomly select 1075 individuals from the dataset with replacement, build our model on the bootstrapped sample and validate it on the original data. We will repeat this process 100 times and include a variable into our final model if it was significant in at least 80 models. We will still emphasise the hypothesis-generating aspect of our findings. We aim to validate our findings in an independent cohort in the future.

6.3. **Sensitivity and subgroup analyses**

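### Section 4.1 derives a threshold of 0.0143 but adopts 0.015, and it leaves the 17 or 22 variables under each primary null uncounted, without saying which step rejects that null

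*SAP*

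**What the plan says.** - **Basis of the adjustment (SAP 4.1).** "We will apply an adjustment for multiplicity based on the total numbers of different primary outcomes tested". In the formula, "α is the unadjusted threshold for significance, usually 0.05", and "m is the number of primary outcomes or tests (used) in the same cohort (in this case: six". The displayed result is 0.0143, which the SAP then equates with 0.015.
- **Use of the threshold (SAP 4.2).** "As calculated in 4.1, we will consider a $P < 0.015$ as statistically significant for our primary outcomes". Intervals are set at 98.5%, and P from 0.015 to 0.05 is labelled dubious. Sections 3.2.1 and 3.2.2 compute power at 0.015.
- **The nulls (SAP 2.2.2).** For the diagnostic study: "Null hypothesis: there is no true correlation between any single or a combination of clinical examination findings and cardiac index measured with CCUS". The prognostic null likewise covers all the variables at once.
- **The tests (SAP 6.2.2 and 6.2.3).** "A univariable regression analysis will be conducted on 17 clinical examination findings with cardiac index as the dependent variable" and "A univariable Cox regression analysis will be conducted on 22 clinical examination, haemodynamic and biochemical variables with 90-day mortality as the dependent variable". The only threshold given for these screens is p<0.25, for entry to the multivariable model.
- **The final model (SAP 6.2.4).** A variable is kept if it is significant in at least 80 of 100 bootstrap models. The significance level for that count is not given.
- **The count of sub-studies (SAP 4.1).** The six outcomes are two from the basic study plus "four additional outcomes in the nine sub-studies". Table 1 and Appendix 1 list eleven sub-studies.

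**The concern.** There are two separate problems. First, the threshold in use is not the one derived: a primary result with P = 0.0145 would be called significant although it fails the SAP's formula. Second, the adjustment deals with multiplicity across outcomes but not within an outcome. A null that says none of 17 (or 22) variables is associated with the outcome can be contradicted by any of them. No overall test and no within-family adjustment is stated, so the error rate attached to rejecting a primary null is undefined. Limiting type I error is one of the aims stated in SAP section 7, which itself acknowledges that many variables will be tested repeatedly.

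**Working it through.** **Inputs.** Alpha 0.05 and m = 6 (SAP 4.1); 17 and 22 variables (6.2.2, 6.2.3); n = 1075, cardiac index SD 0.99, urine output SD 0.98, pilot slope 0.040, target slope 0.10 (3.2.1); 495 and 580 patients with mortality 0.27 and 0.18 (3.2.2). Assumptions: two-sided tests, since sidedness is not stated, and a common correlation from 0 to 0.9, since SAP 5.6 says most variables are correlated but gives no value.

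**1. Threshold.** 0.05/((6+1)/2) = 0.05/3.5 = 0.014286. The SAP's 0.0143 reproduces; 0.015 does not. To obtain 0.015 one would need m = 2 × 0.05/0.015 − 1 = 5.67. The matching interval is 100 × (1 − 0.014286) = 98.57%.

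**2. Effect of the rounding on power** (normal approximation).
- Urine output: residual SD = √(0.99² − (0.040 × 0.98)²) = 0.989. The standardised effect is 0.10 × 0.98 × √1075/0.989 = 3.248. Power at 0.015 is Φ(3.248 − 2.432) = 0.793 (SAP: 0.81). At 0.0143 it is Φ(3.248 − 2.450) = 0.788.
- Mottling: pooled proportion 0.2214, SE 0.02541 under the null and 0.02555 under the alternative. Power at 0.015 is Φ((0.09 − 2.432 × 0.02541)/0.02555) = 0.865 (SAP: 0.84). At 0.0143 it is 0.861.

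The correction costs half a power point or less.

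**3. Any single P<0.015 rejects the global null.** For independent tests the rate is 1 − 0.985^k. For correlated tests it comes from 400,000 draws of equicorrelated normal statistics.

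| Common correlation | 17 variables | 22 variables |
|---|---|---|
| 0 | 22.7% | 28.3% |
| 0.3 | 19.3% | 23.3% |
| 0.5 | 15.0% | 17.6% |
| 0.7 | 10.3% | 11.7% |
| 0.9 | 5.3% | 5.8% |

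At 0.0143 the independent figures are 21.7% and 27.1%, so correcting the rounding alone changes little here.

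**4. The bootstrap rule decides instead.** Treat the bootstrap statistic as normal around the observed one with unit variance, take the chance of at least 80 successes in 100, and average over the null distribution. The rate per variable is 0.00127 if each bootstrap test uses 0.015, and 0.00588 if it uses 0.05. For independent variables:
- level 0.015: 1 − (1 − 0.00127)^17 = 2.1%, and 2.8% for 22 variables;
- level 0.05: 9.5% and 12.2%.

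This is approximate and does not model the p<0.25 screen or the stepwise selection.

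**5. Count of sub-studies.** The distinct outcomes in Table 1 are cardiac output, mortality, StO₂, pulmonary oedema, acute kidney injury and ARDS, which makes six. Sub-studies 1 to 9 add only three of these to the basic study's two; ARDS comes from sub-study 10. So m = 6 stands, but it rests on eleven sub-studies, not nine.

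**The case against.** The strongest reply is that the SAP never states a rule under which one univariable P<0.015 rejects a primary null. The univariable analyses are screens at p<0.25, and the final model is filtered by the bootstrap. A reader might infer that a primary null is falsely rejected 15% to 28% of the time. The documents do not support that as a flat statement: it needs the any-single-variable rule and a correlation no higher than about 0.5, while SAP 5.6 calls most variables correlated. This part of the reply stands. It does not remove the gap, because section 4.2 attaches significance to P<0.015 without linking it to the bootstrap, and sections 3.2.1 and 3.2.2 compute power for one variable at a time at that level.

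A reader might also infer that 0.015 governs every test in the SAP. It does not. Section 4.2 ties it to the primary outcomes; screening uses 0.25, and the proportional-hazards and Little's tests use 0.05. Appendix 1 sections 2.5, 9.5 and 10.5 pair 0.015 with Z = 2.17, which corresponds to two-sided 0.03. Nor is m itself wrong: section 4.1 bases it on distinct primary outcomes, and six is the correct count.

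Finally, the results are to be presented as hypothesis-generating, with independent validation intended (6.2.4, 7), and there is a dubious band for P between 0.015 and 0.05. This lowers the stakes, but the label statistically significant is still applied below 0.015.

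**Conclusion.** The point holds in two parts of unequal weight. The rounding is a plain error of small size: 0.015 is 5% above 0.014286 (0.015/0.014286 = 1.05), and correcting it costs half a power point or less. The main matter is that the six-outcome adjustment does not cover the 17 or 22 variables under each global null and no rejecting step is named. Depending on the step, the rate is 5% to 28% (any single variable, correlation 0.9 down to 0) or roughly 2% to 12% (bootstrap rule, independent variables).

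Every figure calculated exceeds 0.015. The bootstrap figures assume independence, however, and correlation would lower them, towards the single-variable rate of 0.0013 to 0.0059 at the extreme. It would therefore go too far to say that the error rate must exceed 0.015 under every reading. What can be said is that the SAP does not fix it. The count of nine sub-studies is a wording error that leaves m unchanged.

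**What to change.** 1. Use 0.0143 (or 0.014) and 98.6% intervals for the primary outcomes, and restate the basic-study power figures at that level.
2. Name one test that rejects each primary null at that threshold. Either:
   - use the overall F-test of the 17-finding linear model and a global test of the 22 variables against a null Cox model; or
   - use Holm-adjusted P-values within each family, whose first step tests the global null, at 0.0143/17 = 0.00084 and 0.0143/22 = 0.00065.

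   State whether the bootstrap rule has any part in that decision, and at what significance level it runs. Report any comparison with SAPS-II alone separately: it measures added value, not the no-association null of section 2.2.2.
3. Correct nine sub-studies to eleven; m = 6 is unchanged.

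**Cost.** Wording and two pre-specified tests or adjustments. Some single variables near the threshold lose the label significant. Under Holm's first step, the approximation above gives power for the SAP's own examples of about 0.46 for urine output (Φ(3.248 − 3.339)) and 0.55 for mottling (Φ((0.09 − 3.410 × 0.02541)/0.02555)). The overall tests avoid that penalty for the global null. The 22-variable Cox test would, however, need 22 × 15 = 330 events if the events rule in section 6.2.3, which is written for the final model, were applied to it. If the 0.28 control mortality in Appendix 1 section 4.5 held for the whole cohort (an assumption), 1075 patients would give 0.28 × 1075 = 301. Holm does not depend on fitting that model.
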